For Cohort 2, Study drug is to be applied to the wart site on any Treatment Visit where a new clinical assessment of complete clearance is made for that wart (e.g., if a patient returns for Treatment Visit 2 and is clinically assessed to have no visible evidence of remaining wart, then Study drug is to be applied to this wart site at Treatment Visit 2. However, if the patient remains completely clear at that wart site when returning for Treatment Visit 3, then no Study drug would be applied at Treatment Visit 3.)

In instances where the clinician can adequately assess the treatment sites but is uncertain if residual wart is remaining, treatment should be applied, and the subject should return for evaluation per protocol. Treatment visits are to take place in order (e.g., Treatment 1, Treatment 2, Treatment 3 and Treatment 4). Subjects that receive fewer than 4 treatments within the 63-day (Cohort 1) or 75-day (Cohort 2) treatment period, due to the duration of post-treatment local skin reactions, will not be considered a protocol deviation. No treatment should be administered after the 63-day treatment period in Cohort 1 or the 75-day treatment period in Cohort 2 without Sponsor’s approval. Subjects in Cohort 1 that achieve complete clearance of all treatable warts prior to Treatment Visit 4, will receive ERT phone calls at the required 2-week treatment intervals to assess the status of any AEs or skin reactions since the last visit and confirm there has been no recurrence or development of new warts. In the event warts are present, the subject will be scheduled for a Treatment Visit per protocol. *(Consider calling the subject a few days prior to the 2-week interval (e.g., 11 or 12 days) to ensure adequate time for scheduling assessment and treatment if needed).*

Subjects participating in Cohort 2, will be required to attend all visits regardless of whether they have achieved complete clearance of all warts at a previous visit. At these visits, Study drug application is not required if the warts have been clear for at least one follow up visit and the investigator determines that additional treatment is not needed. Subjects participating in Cohort 2, that have completed their Day 84 EOT Visit (- 0/+ 8 days), will be assessed at 3 additional follow-up visits conducted at Day 105, Day 126 and Day 147.

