All subjects will receive application of the Study drug (VP-102) to common warts including a 1-2 mm margin of healthy, surrounding skin with an interval of at least 14 days in Cohort 1, and every 21 days in Cohort 2, until complete clearance of all treatable warts, or a maximum of 4 applications. Warts are to be treated and then occluded with transparent surgical tape (e.g.; 3M™ Blenderm™ brand) that will remain on overnight and removed just prior to the 24-hour ERT phone call. Subjects in Cohort 2 will undergo wart paring with a sharp surgical instrument (e.g., scalpel or flexible medical blade) to remove any adherent thick scale from a wart prior to application of Study drug. Wart paring is to be performed at any Treatment Visit when adherent thick scale is present, and the investigator considers that it can be safely applied. Paring should be conducted by a trained practitioner and in compliance with any local regulations and should be discontinued when it results in punctate bleeding or significant pain. Not all warts may require paring and if adherent scale is not present, then Study drug can be applied without paring. Subjects should be re-treated only after 14-

days have elapsed in Cohort 1 and 17 days (i.e., 21 +/- 4 days) have elapsed in Cohort 2, but only after any LSR has resolved sufficiently to allow evaluation of the treatment site. . Subjects that achieve complete clearance of all treatable warts prior to the EOS visit, return to the clinic for a EOS/EOT visit at Day 84 in both Cohorts. Subjects in Cohort 2 are to attend all visits regardless of whether they have achieved complete clearance prior to the Day 84 (- 0/+ 8 days) assessment. Phone calls will be conducted at an interval of 24 hours and 7 days after each Treatment Visit (not “Unscheduled” visits) to assess if there have been any adverse events or if new warts have occurred. Phone calls conducted outside of the required 24-hour and 7-day study ERT assessments should be documented in the subject’s source note but are not required to be entered into the electronic data capture (EDC). All required study activities, including ERT evaluations, will be conducted per protocol. If new warts are identified during the course of the treatment period, they should be documented, evaluated and treated per protocol.

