- Photos taken by subject (per protocol Cohort 1 & 2) Treatment Visit 4:
 - Wart count (Cohort 1),
 - Measurement and location of all warts,
 - Photos (if applicable),
 - Dermatologic exam, ERT,
 - Paring of warts (Cohort 2), if applicable,
 - Study drug application and occlusion with tape (if subject has warts remaining),
 - Removal of occlusive tape and Study drug 24 hours after application,
 - ERT phone call at 24h and day 7,
 - Any new warts should be counted (Cohort 1), measured, documented and treated per protocol,
 - ERT and wart count (Cohort 1) conducted over the phone if cleared at Treatment Visit 3,
 - Photos taken by subject (per protocol Cohort 1 & 2).
- **“Unscheduled” Visit:** May take place at any time, as needed, to evaluate the subjects for safety reasons or for those subjects unable to be treated due to an ongoing LSR. For those subjects evaluated at their scheduled Treatment Visit as exhibiting untreatable warts, no treatment will be administered, and an “Unscheduled” treatment form will be completed. The following information should be obtained:
 - Reason treatment was not administered,
 - Dermatologic exam,
 - ERT, including LSR, wart count (Cohort 1) and location of all warts,
 - Photos (if applicable).
- **Cohort 1: End of Study Visit (EOS Day 84); Cohort 2: End of Treatment Visit (EOT; Day 84)**In person: Vital signs, weight, wart count (Cohort 1),
 - Measurement and location of all warts,
 - Photos (if applicable),
 - Dermatologic exam and ERT,
 - Any new warts should be counted (Cohort 1), measured and documented per protocol,
 - Provider EOS/EOT Treatment Questionnaire.
- **Follow-up Visits Cohort 2: (Day 105, Day 126 and Day 147)**
 - In person: Vital signs,
 - Measurement and location of all warts,
 - Photos (if applicable),

- Dermatological exam and ERT,
- Any new warts should be measured and documented per protocol.

Study Duration:

Cohort 1: Study duration from Treatment Visit 1 through the EOS is approximately 84 days (12 weeks, may extend up to 98 days). No treatment should be administered after Day 63 without Sponsor's approval.

Cohort 2: Study duration from Treatment Visit 1 through the final follow-up is approximately 147 days (21 weeks). No treatment should be administered after Day 75 without Sponsor's approval. Post-treatment follow-up visits are included for subjects in Cohort 2 to evaluate the durability of treatment response over time.

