Subject Participation: Pre-study screening for eligibility (informed consent and assent [when applicable]), demographics, physical exam, prior and current concomitant medications and medical history can occur up to 14 days before, or on the same day as the first Study drug application. The dermatologic exam, wart count (Cohort 1), measurements, location of all warts, ERT and photos must be repeated if not conducted on the same day as treatment. Warts must measure at ≤ 10 mm in diameter and ≤ 3 mm in height for both Cohorts (paring can be performed, if necessary, in Cohort 2 prior to assessing height for inclusion).

Subjects that do not continue to meet criteria at Treatment Visit 1 will be discontinued and treated at physician discretion per standard of care. Those subjects that meet the enrollment criteria will be treated with application of VP-102 at Treatment Visit 1. Treatment will continue with a minimum of 14 days, in Cohort 1, and every 21 (+/- 4 days), in Cohort 2, until complete clearance or a maximum of 4 treatment sessions. The exact treatment interval will be determined by evaluation of the treatment site and take any ongoing LSRs into account. In Cohort 1, subjects that achieve complete clearance of all treatable warts prior to Treatment Visit 4, will receive ERT phone calls at the required 2-week treatment intervals to assess the status of any Aes or skin reactions since the last visit and confirm there has been no recurrence in treated warts or new warts have developed. Subjects that report recurrence of, or presence of new warts, will be scheduled for a Treatment Visit per protocol. (*Consider calling the subject a few days prior to the 2-week interval (e.g., 11 or 12 days) to ensure adequate time for scheduling assessment and treatment if needed.*)

For those enrolled in Cohort 2, subjects will be required to return for every treatment and follow-up visit whether or not their warts have cleared. Phone follow-ups will be conducted per protocol for those instances where the subject was treated.

Inclusion criteria:

To qualify for inclusion in this study, subjects must:

1. Be healthy, immunocompetent males or females at least 2 years of age and older for Cohort 1 and 12 years of age and older for Cohort 2.

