It can sometimes be challenging to determine if a wart is completely clear after treatment due to ongoing local skin reactions. At any visit where the investigator is unable to evaluate or treat some warts due to ongoing local skin reactions, an "Unscheduled" Visit should be documented. The timing of the next visit will be determined by the resolution of the local skin reaction. A Treatment Visit should be documented at every visit where Study drug is applied. Treatment should only take place at a visit when all warts are evaluable (i.e., not obscured by an ongoing LSR) and all warts that are not completely clear, should undergo treatment with Study drug. No partial treatment of warts is permitted.

For Cohort 2, Study drug is to be applied to the wart site on any Treatment Visit where a new clinical assessment of complete clearance is made for that wart (*e.g., if a patient returns for Treatment Visit 2 and is clinically assessed to have no visible evidence of remaining wart, then Study drug is to be applied to this wart site at Treatment Visit 2. However, if the patient remains completely clear at that wart site when returning for Treatment Visit 3, then no Study drug would be applied at Treatment Visit 3.*) Should it become clear that the subject will be unable to complete the EOS visit within the allowed window of Day 84 (- 0/+ 8) days, the subject should be brought in for their EOS visit as soon as they are able. This will be documented as a protocol deviation.

In instances where the clinician can adequately assess the treatment sites but is uncertain if residual wart is remaining, treatment should be applied, and the subject should return for evaluation per protocol. Treatment visits and assessments are to take place in order (e.g., Treatment 1, Treatment 2, Treatment 3 and Treatment 4). Subjects that receive fewer than 4 treatments within the 63-day (Cohort 1) or 75-day (Cohort 2) treatment period, due to the duration of post-treatment local skin reactions, will not be considered a protocol deviation. No treatment should be administered after the 63-day treatment period in Cohort 1 or the 75-day treatment period in Cohort 2 without Sponsor's approval.

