6 EXPERIMENTAL PROCEDURES

6.1 Overview: Schedule of Time and Events

Each subject will be evaluated and treated as follows:

- **Screening Period** (Up to 14 days prior to first treatment)
- **Safety Evaluation Period** (Treatment Visit 1)
 - Confirm that subject still meets enrollment criteria (dermatologic exam; ability to attend study visits),
 - Wart count (Cohort 1)
 - Measurement of each wart size (diameter, height) and location,
 - Photos of all warts if applicable,
 - Paring of warts (Cohort 2), if applicable,
 - Study drug application and occlusion with occlusive tape,
 - Removal of occlusive tape and Study drug 24 hours after application,
 - 24-hour and 7-day ERT phone call,
 - Photos taken by subject at home every 24hours for 5 days if applicable (Cohort 1),
 - Photos taken by subject at home at 24 hours (Cohort 2).
- **Safety and Efficacy Evaluation Period** (visits targeted at least 14 days after prior treatment in Cohort 1 and every 21 +/- 4 days in Cohort 2)
- **Treatment Visit 2:**
 - Wart count (Cohort 1),
 - Measurement and location of all warts,
 - Paring of warts (Cohort 2), if applicable,
 - Photos (if applicable),
 - Dermatologic exam, ERT,
 - Study drug application and occlusion with tape (if subject has any warts remaining). Removal of occlusive tape and Study drug 24 hours after application.
 - ERT phone call at 24h and day 7,
 - Any new warts should be counted (Cohort 10, measured, documented and treated per protocol,
 - Photos taken by subject (per protocol Cohort 1 & 2).
- **Treatment Visit 3:**
 - Wart count (Cohort 1),
 - Measurement and location of all warts,
 - Paring of warts (Cohort 2), if applicable,
 - Photos (if applicable),

- Dermatologic exam, ERT,
 - Study drug application and occlusion with tape (if subject has warts remaining),
 - Removal of occlusive tape and Study drug 24 hours after application,
 - ERT phone call at 24h and day 7,
 - Any new warts should be counted (Cohort 1), measured, documented and treated per protocol,
 - ERT and wart count (Cohort 1) conducted over the phone if cleared at Treatment Visit 2,
- Photos taken by subject (per protocol Cohort 1 & 2). Treatment Visit 4:
 - Wart count (Cohort 1),
 - Measurement and location of all warts,
 - Photos (if applicable),
 - Dermatologic exam, ERT,
 - Paring of warts (Cohort 2), if applicable,
 - Study drug application and occlusion with tape (if subject has warts remaining),
 - Removal of occlusive tape and Study drug 24 hours after application,

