Subjects in Cohort 2 will undergo wart paring with a sharp surgical instrument (e.g., scalpel or flexible medical blade) to remove any adherent thick scale from a wart prior to application of Study drug. Wart paring is to be performed at any Treatment Visit when adherent thick scale is present, and the investigator considers that it can be safely applied. Paring should be conducted by a trained practitioner and in compliance with any local regulations and should be discontinued when it results in punctate bleeding or significant pain. Not all warts may require paring and if adherent scale is not present, then Study drug can be applied without paring.

Subjects that do not continue to meet criteria at Treatment Visit 1 will be discontinued and treated at physician discretion per standard of care. Those subjects that meet the enrollment criteria will be treated with application of VP-102 at Treatment Visit 1. Treatment will continue with an interval of at least 14 days in Cohort 1, and 21 days in Cohort 2, between treatments until complete clearance or a maximum of 4 treatment sessions. Subjects should be re-treated only after 14 days have elapsed in Cohort 1 or 21 (+/- 4 days) in Cohort 2, but only after any LSR has resolved sufficiently to allow evaluation of the treatment site. The research team should be in contact with the patient until LSRs are resolved and Treatment Visit can be scheduled within 14 days for Cohort 1 and 21 days (+/- 4) for Cohort 2, when possible. Treatment should be administered within 4 days of becoming eligible due to resolution of LSRs. Treatment will be applied up to four times during a 63-day treatment period for Cohort 1 and

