It can sometimes be challenging to determine if a wart is completely clear after treatment due to ongoing local skin reactions. At any visit where the investigator is unable to evaluate or treat some warts due to ongoing local skin reactions, an “Unscheduled” Visit should be documented. The timing of the next visit will be determined by the resolution of the local skin reaction. A Treatment Visit should be documented at every visit where Study drug is applied. Treatment should only take place at a visit when all warts are evaluable (i.e., not obscured by an ongoing LSR) and all warts that are not completely clear, should undergo treatment with Study drug. No partial treatment of warts is permitted.

For Cohort 2, study drug is to be applied to the wart site on any Treatment Visit where a new clinical assessment of complete clearance is made for that wart (e.g., if a patient returns for Treatment Visit 2 and is clinically assessed to have no visible evidence of a remaining wart, then Study drug is still to be applied to this wart site at Treatment Visit 2. However, if the patient remains completely clear at that wart site when returning for a subsequent visit such as Treatment Visit 3, then no Study drug would be applied at Treatment Visit 3.) Should it become clear that the subject will be unable to complete the EOT visit within the allowed window of Day 84 (+/- 8) days, the subject should be brought in for their EOT visit as soon as they are able. This will be documented as a protocol deviation.

In instances where the clinician can adequately assess the treatment sites but is uncertain if a residual wart is remaining, treatment should be applied, and the subject should return for evaluation per protocol. Treatment visits and assessments are to take place in order (e.g., Treatment 1, Treatment 2, Treatment 3 and Treatment 4). Subjects that receive fewer than 4 treatments within the 75-day (Cohort 2) treatment period, due to the duration of post-treatment local skin reactions, will not be considered a protocol deviation. No treatment should be administered after the 75-day treatment period in Cohort 2 without Sponsor’s approval.

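### Cohort 2 visit lists and stopping text omit the required application to a newly cleared wart site, and contradict it when all of a subject's warts are clear

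*Protocol*

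**What the plan says.** The Cohort 2 rule appears in three places. Protocol Section 4.1, and the Synopsis in the same words, state: "Study drug is to be applied to the wart site on any Treatment Visit where a new clinical assessment of complete clearance is made". Both give a worked example: no visible wart at Treatment Visit 2, so treat; still clear at Visit 3, so do not. SAP Section 3 repeats the example more firmly: "then Study drug is still to be applied to this wart site at Treatment Visit 2". The Synopsis and Section 4.1 also say when drug may be withheld at a Cohort 2 visit: "if the warts have been clear for at least one follow up visit and the investigator determines that additional treatment is not needed".

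Two groups of text leave the rule out.

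- **Visit lists.** In Protocol Section 6.1 and the Synopsis, the Treatment Visit 2 line is "Study drug application and occlusion with tape (if subject has any warts remaining". The Visit 3 and 4 lines read "Study drug application and occlusion with tape (if subject has warts remaining". The lists serve both cohorts and tag other items by cohort (wart count, paring), but not the application line.
- **Stopping text that names Cohort 2.** The Synopsis (Methodology) and Section 4.1 have "and every 21 days in Cohort 2, until complete clearance of all treatable warts, or a maximum of 4 applications". The Synopsis (Subject Participation) has "in Cohort 2, until complete clearance or a maximum of 4 treatment sessions". Section 6.1 has "and 21 days in Cohort 2, between treatments until complete clearance or a maximum of 4 treatment sessions". Section 5.2, the dosing section, is to the same effect.

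Item 9 of Section 6.2.3 tells staff to treat all warts, including new ones. It sets no stopping rule and does not mention newly cleared sites. No text says which statement governs.

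**The concern.** This is a dosing instruction, and the parts of the protocol that site staff use visit by visit do not contain it. Section 8.1.3 makes Section 5 the reference for judging whether a subject received treatment as mandated, and Section 5.2 stops at clearance without the Cohort 2 exception.

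A site working from Section 5.2 or the Section 6.1 lists would give a newly fully clear subject one application fewer than the regimen Cohort 2 is meant to evaluate. A site working from Section 4.1 would give the full regimen. The Synopsis says the clearance rates should inform assumptions for later placebo-controlled trials, and that post-treatment follow-up is there to judge durability. Both uses need one known regimen. Local skin reactions are recorded as adverse events, and SAP Section 10.1 tabulates the number of treatment visits, so the safety and exposure summaries could also mix two regimens.

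**Working it through.** The plan gives no figure to reproduce: the study is descriptive and has no power calculation. The check is a comparison of texts, followed by simple date arithmetic.

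**Step 1: where the texts conflict.** The rule works per wart site. The visit-list condition works per subject.

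| Situation at a Treatment Visit (2 to 4) | Rule (Section 4.1, Synopsis, SAP Section 3) | Visit lists |
|---|---|---|
| Some warts remain, one site newly clear | Treat the newly clear site | Application goes ahead; silent on the newly clear site |
| All warts clear, at least one newly clear | Treat the newly clear site | No application: direct contradiction |
| All warts clear, all already clear at the previous visit | Not required if the investigator agrees | No application: consistent |

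Only the second row is a contradiction for the lists. In that row the stopping text also ends treatment. The Synopsis (Methodology) and Section 4.1 refer to clearance of all treatable warts; the other three statements say only complete clearance.

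The passage in Sections 4.1 and 6.1 on treating when residual wart is uncertain does not close the gap. It concerns doubt, not a site judged clear.

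**Step 2: size per affected subject.** Inputs:

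- Treatment 1 on Day 1 (Protocol Table 2).
- Planned Days 21, 42 and 63 for the next three visits (SAP Section 8).
- End of treatment on Day 84.
- Treatment interval 21 +/- 4 days (Protocol Table 2).

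Drug-free interval = 84 minus the day of the last application.

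| All warts first seen clear at | Lists: applications, interval | Rule: applications, interval | Difference |
|---|---|---|---|
| Treatment Visit 2 | 1; 84 - 1 = 83 days | 2; 84 - 21 = 63 days | 20 days (20/63 = 32%) |
| Treatment Visit 3 | 2; 84 - 21 = 63 days | 3; 84 - 42 = 42 days | 21 days (21/42 = 50%) |
| Treatment Visit 4 | 3; 84 - 42 = 42 days | 4; 84 - 63 = 21 days | 21 days (21/21 = 100%) |

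The difference is always one treatment interval. Within the protocol window that is 21 - 4 = 17 to 21 + 4 = 25 days, and longer if a local skin reaction delays the visit.

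**Step 3: what cannot be computed.** The documents do not say how many of the approximately 35 subjects would be first seen fully clear at Treatment Visits 2 to 4, which text sites followed, or what one application does to clearance. No effect on the Day 84 rate can be estimated.

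**The case against.** The strongest defence is that a specific rule displaces a general one. The rule is headed for Cohort 2, comes with an example, is reinforced by the condition for withholding drug, and is repeated in the SAP. The contrary lines are shared bullets under an overview heading, or phrases that mainly set the interval and the four-application cap. That is a sensible reading and supports keeping the rule. It remains an inference, and staff would have to make it from sections that never mention the rule.

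Table 2 marks application at Treatments 1 to 4 with no condition about remaining warts. This gives little help, because Table 1 marks Cohort 1 in the same way.

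The Instructions for Use and manual of operations may carry the rule. They are not available here, so this can neither be relied on nor excluded.

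An omitted application would show in the data, because SAP Section 10.1 counts treatment from a per-wart question at each visit. That makes mixed dosing visible; it does not prevent it.

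A reader might infer that SAP Section 8 is another contrary rule, since it describes treatment as continuing while warts are present. The documents do not support that. The clause introduces the naming of visits. The same section records clearance as a 0 mm diameter and keeps the cleared check box for later visits. It then names as Treatment Visits those where treatment was given or every wart has that box marked. A visit where clearance is new is therefore named through the treatment given there, which fits the rule.

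**Conclusion.** The inconsistency is real and worth correcting, within limits. For the visit lists it is a direct contradiction only when all of a subject's warts are clear and at least one is newly clear; otherwise they are silent on newly cleared sites. In the contradictory case, following the lists or Section 5.2 costs one application and lengthens the drug-free interval before Day 84 by one treatment interval: 20 or 21 days on planned days, 17 to 25 within the window. This assumes that staff act on those sections as written and that no site document corrects them.

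Stronger conclusions are tempting but not supported:

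- **A compromised primary analysis.** The endpoint definition, ITT population, missing-as-failure rule and day-based visit windows are untouched, and no bias in the clearance rate can be derived.
- **Loss from the Per Protocol population.** SAP Section 6 accepts subjects cleared before Day 75. It also lists dosing errors among the criteria for major deviations, subject to clinical review. It does not say how this omission would be classed, so no effect is claimed.
- **Loss of safety calls.** Table 2 footnote m ties the phone assessments to visits where drug is applied, but Section 4.3.1 says the response assessments are done whether or not treatment is applied. A loss is not established.

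**What to change.** Keep the rule and the investigator discretion in the Synopsis and Section 4.1, and point the other text to them.

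1. In the Treatment Visit 2 to 4 application lines of the Synopsis and Section 6.1, and in item 9 of Section 6.2.3, add: *(Cohort 2: also to any wart site newly assessed as completely clear at this visit; see Section 4.1)*.
2. In the stopping text of the Synopsis (Methodology and Subject Participation) and Sections 4.1, 5.2 and 6.1, add: *except that in Cohort 2 drug is also applied to any wart site at a Treatment Visit where it is newly assessed as completely clear, within the maximum of 4 applications (see Section 4.1)*.
3. Do not limit the exception to one further dose or to the first time a site clears. The rule is triggered by any new assessment of clearance, and SAP Section 8 foresees warts that return, so a site that recurs and clears again is covered.
4. SAP Section 8 needs at most a cross-reference to SAP Section 3.
5. Align the Instructions for Use and manual of operations with the rule, and notify sites.

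The cost is wording in the protocol, at most one line in the SAP, a check of the site documents and one site clarification. The endpoint, sample size, analysis populations and missing-data rules do not change.
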